7.6.10.2 Sample Collection, Storage, and Shipping

A study-specific laboratory manual will detail sample collection, storage, and shipping procedures. Serum or plasma samples will be stored at least one year after the date of database lock.

Blood and urine samples except for the dipstick urinalysis, will be collected by the Investigator or designee at specified time points and sent to a central laboratory for processing. Details about the central laboratory are provided in Section 10.1.

7.6.11 Adverse Events Assessments

7.6.11.1 Performing Adverse Events Assessments

An AE is defined as any untoward medical occurrence in a subject administered a pharmaceutical product (including investigational drug) during the course of a clinical investigation. An AE can, therefore, be any unfavorable and unintended sign (including an abnormal laboratory finding), symptom, or disease temporally associated with the use of an investigational product, whether or not considered related to the investigational product.

The AEs will be found by the subject's spontaneous complaint, or as a result of non-leading questions, physical examination, vital signs, laboratory tests, or other procedures.

The AEs include any occurrences that are new in onset or aggravated in severity or frequency from the baseline condition, or abnormal results of diagnostic procedures, including laboratory test abnormalities. Conditions reported as medical history at baseline that worsen during the course of the study will be considered AEs. Lack of efficacy determined by progression of symptoms of vaginal dryness, or dyspareunia are not AEs in this study.

The AEs resulting from concurrent illnesses, concomitant medications, or progression of disease states must also be reported. A procedure should not be reported as an AE; only the condition for which the procedure is required should be reported as an AE if it is new or is a worsening of a pre-existing condition. Elective procedures for which the underlying condition was present at screening and has not worsened, do not constitute an AE.

The Investigator or Sub-investigator is responsible for assessing AEs. AEs should be fully investigated and recorded in detail including onset date, end date (if outcome is other than not recovered, recovering, or unknown), severity, relationship with the study drug, action taken due to the AE, and outcome of the AE in the eCRF.

7.6.11.2 Timing

All AEs will be collected from the time of informed consent through the Follow-Up call. If a subject withdraws early from the study, the Investigator or Sub-investigator will make an effort to collect AEs for 2 weeks after the last dose of study drug. Any AE or SAE ongoing 2 weeks after the last dose of study drug will be followed until resolution, stabilization, the condition becomes chronic, or the subject is lost to follow-up.

7.6.11.3 Severity

The severity of an AE will be graded by the Investigator or Sub-investigator according to the following definitions:

- Mild: A finding or symptom is minor and does not interfere with usual daily activities.
- Moderate: The event is uncomfortable and causes interference with usual daily activity or affects clinical status.
- Severe: The event causes interruption of the subject's usual daily activities or has a clinically significant effect.

The highest severity during the period when the AE occurred will be recorded in the eCRF.

7.6.11.4 Relationship

The relationship (causality) of AE to the study drug should be determined by the Investigator according to the following criteria:

- **Related:** An AE for which causal relationship with the study drug can be reasonably explained. For example, the occurrence of the AE cannot be explained by other causative factors, the AE can be explained by the pharmacological effect of the study drug (eg, a similar event had been reported previously), or increase/decrease of the dose affect the characteristics of the AE (rechallenge/dechallenge), etc.
- **Not Related:** An AE for which causal relationship with the study drug cannot be reasonably explained.

7.6.11.5 Expectedness

An AE is expected if it is listed in the Adverse Reactions Section of the current ospemifene U.S. package insert.

7.6.11.6 Action Taken

Any action taken with regard to study drug as a consequence of an adverse experience, drug withdrawn, drug interrupted, dose not changed or not applicable, should be captured in the eCRF.

7.6.11.7 Laboratory Adverse Events

Abnormal laboratory test results are defined as having a value outside the reference range. For laboratory test results which are normal at baseline and become abnormal following initiation of the study or results which are abnormal at baseline and significantly worsen following the initiation of the study, the Investigator or Sub-investigator must also consider whether the results are clinically significant. Any test results considered clinically significant by the Investigator or Sub-investigator should be considered for reporting as AEs. If an abnormal laboratory finding is associated with other clinical findings for which a diagnosis can be provided, the Investigator should report only the diagnosis (and not the laboratory abnormality) as AEs.

The Investigator or Sub-investigator will consider a test result clinically significant if the test result:

- Leads to any of the outcomes included in the definition of an SAE (See Section 7.6.11.8).
- Leads to discontinuation from the study.
- Leads to a concomitant drug treatment or other therapy.
- Requires additional diagnostic testing or other medical intervention.
- Meets the management and discontinuation criteria for abnormal liver function tests (LFTs) identified in Appendix 10.

In addition, when any test result meets the management and discontinuation criteria for liver function abnormalities (Appendix 10), the results of further assessments and required follow-up should be recorded in the Liver Event Form.

7.6.11.8 Serious Adverse Events

Definition

An SAE is defined by regulation as any AE occurring at any dose that results in any of the following outcomes:

- Death
- Life-threatening condition
- Hospitalization or prolongation of existing hospitalization for treatment
- Persistent or significant disability/incapacity
- Congenital anomaly/birth defect
- Other medically important conditions that may not result in death, be life threatening, or require hospitalization may be considered an SAE when, based upon appropriate medical judgment, they may jeopardize the subject's health and may require medical intervention to prevent one of the outcomes listed in the above definition. Examples of such medical events include allergic bronchospasm requiring intensive treatment in an emergency room or at home, blood dyscrasias or convulsions that do not result in inpatient hospitalization, or the development of drug dependency or drug abuse.

The Investigator or Sub-investigator will determine the seriousness of AEs. Test results that meet the following Hy's law criteria are considered SAEs.

- AST or ALT $>3 \times$ ULN and total bilirubin (TBL) $>2 \times$ ULN

Reporting Serious Adverse Events

All SAEs must be reported to the Sponsor in detail on the SAE form within 24 hours from the point in time when the Investigator first becomes aware of the SAE. All SAEs must be reported regardless of causal relationship to the study drug. A sample of the SAE form can be found in the Site Regulatory Binder. Follow-up information about the SAE may be requested by the Sponsor.

When reporting SAEs, the Investigator should record the diagnosis whenever possible. If no diagnosis is available at the time of reporting, individual signs and symptoms can be reported.

In the event of any SAE reported or observed during the study, whether or not attributable to the study drug, site personnel must prepare an SAE Form and submit the completed form within 24 hours to:

UBC Hotline

Tel: PPO

Email: PPO

Fax: PPO

If follow-up is required or requested, the Investigator should provide new information to the Sponsor's medical monitor as it becomes available using the SAE Form, then it should be submitted. Discharge summaries, consultant reports, autopsy reports, and/or other relevant documents must be evaluated by the Investigator and all relevant information must be included on the follow-up SAE form. Copies of these reports may also be requested by the Sponsor.

Appropriate remedial measures should be taken by the Investigator using his/her best medical judgment to treat the SAE. These measures and the subject's response to these measures should be recorded. Clinical, laboratory, and diagnostic measures should be used by the Investigator as needed to adequately determine the etiology of the event.

Any SAE that occurs after the AE assessment period specified in Section 7.6.11.2 that is considered by the Investigator to be related to study drug must be reported to the Sponsor.

The Investigator will be responsible for reporting all SAEs to the IRB. The Sponsor will be responsible for reporting SAEs to the regulatory authorities, as required by the applicable regulatory requirements.

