- l May be omitted in subjects with a normal mammogram within 9 months prior to screening for which the results are available.
- m To be assessed based on pill count. When there is a discrepancy between the pill count and the subject-reported compliance, the subject-reported compliance should be used.
- n Do not perform if discontinuation (early termination) occurs PRIOR to VISIT 5 (Week 12).
- o Repeat after cure of infection at V1.

- p Repeat after cure of infection at V2.
- q Follow-up call should occur ON Day 14 after last dose. In case subject does not respond, three follow-up attempts should be made.

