5.9 Treatment Compliance

The Investigator and/or study personnel will assess treatment compliance at each visit using pill counts and information provided by the subject. The Investigator should stress to the subject the importance of compliance and ensure that she understands the dosing instructions. Compliance checks by tablet count will be performed by qualified site

personnel in order to verify that the correct number of doses have been taken based on the actual number of days that have elapsed between designated clinic visits.

A record of the study drug taken by the subject will be made in the eCRF as required. In the event of discrepancy between the tablet count and the information provided by the subject, the information provided by the subject will be recorded in the eCRF.

Based on compliance checks, a subject will be counseled by the site about the importance of taking the study drug as directed if < 100% of the required study drug has been taken by that subject. If compliance issues persist and overall dosing compliance is < 80%, the Investigator may consider discontinuing the subject from the study.

In the event a subject has interrupted or discontinued study drug, the subject must inform the Investigator and the rationale must be provided in the source document. The subject may continue in the study after agreement with the Investigator. If the study drug has been temporarily discontinued for safety reasons, the Investigator must document the reasons in the source document and discuss with the medical monitor prior to the subject reinitiating study drug. All interruptions of study drug (≥ 1 day) should be captured in the eCRF.

In the event a subject is withdrawn for compliance reasons (eg, missed doses or visits), the Investigator will notify the Sponsor or designee promptly and will make every effort to complete the early termination assessments and the Completion/Discontinuation eCRF. The Investigator must register all subject discontinuations in the IxRS.

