7.6.11.10 Treatment-Emergent Adverse Events

AEs reported after the initial dose of randomized study drug will be considered treatment-emergent adverse events (TEAE).

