9.11 Safety Analyses

9.11.1 Adverse Events

AEs will be classified by system organ class and preferred term using the Medical Dictionary for Regulatory Activities (MedDRA). Of the AEs reported in the eCRF, TEAEs will be used for safety analyses. The definition of TEAE is described in Section 7.6.11.10.

The number of subjects who experience ≥ 1 TEAE, non-fatal treatment-emergent SAEs, significant TEAEs, TEAEs leading to withdrawal, and TEAEs with an outcome of death will be counted for each treatment group. The incidences and their 95% confidence intervals (CIs) will be calculated using the Clopper-Pearson method. The number of TEAEs counted by cases reported will also be presented. Treatment-related TEAEs will be summarized by the same category as TEAEs in the overall summary.

A summary of TEAEs by MedDRA system organ class and preferred term will be presented for each treatment group with the number and percent of subjects. A summary of severity and outcome will be presented by system organ class and preferred term.

All AEs, including AEs that existed prior to or after the first dose of the study drug, will be listed. AEs reported with an onset date prior to randomization of study drug will be listed separately.

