10.1 Adverse Events

All adverse events (AEs) will be collected from the time of informed consent through 14 days after the last dose of study medication. All AEs will be classified by SOC and PT using MedDRA Version 18.0 and presented in subject listings.

AEs that occurred from the first dose of study medication up to 14 days after the last dose will be considered treatment-emergent AEs (TEAEs). Only TEAEs will be counted in the summary tables described below. If more than one AEs that map to the same SOC or the same PT are occurred in a subject, the subject will be counted only once at each level of summarization (i.e., SOC level or PT level) using AE with the strongest outcome and/or severity.

If partial dates of onset are missing, the following imputation algorithm will be applied;

- If the information of period of onset is 'After first dose of study drug' and the month of onset is same as the first dosing date but day is unknown, the day will be same as the first dosing date.
- If the information of period of onset is 'After first dose of study drug' and the month of onset is different from the first dosing date but day is unknown, the day will be first day of the month.

All AEs will be listed. TEAEs will be summarized as assessments of short term safety and long term safety, separately. For assessment of short term safety, following TEAEs will be included;

- if a subject takes study medication for more than 12 weeks (beyond Visit 5), AEs that occurred until Visit 5 will be summarized;
- if a subject takes study medication for 12 weeks or less than 12 weeks, all TEAEs will be summarized.

For assessment of long term safety, the target safety population will be limited to subjects who continue to Part B in two previous protocols (original protocol:06Oct2012 and protocol amendment 1: 11Mar2016) and take study drugs more than 12 weeks (beyond Visit 5) and TEAEs after 12 weeks (beyond Visit 5) will be summarized.

The following summary tables of TEAEs will be produced:

1) Overview of Adverse Events

For each treatment group, the number of events and subjects who experience

- TEAEs
- Serious TEAEs
- TEAEs leading to withdrawal
- TEAEs with an outcome of deaths

will be counted and the incidence proportion will be calculated for each treatment group. The difference in the incidence proportion and its 95% confidence interval (CI) will also be calculated. Treatment-related AEs will be summarized by the same category as TEAEs, except for death.

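### SAEs that start more than 14 days after the last dose are treatment-emergent under the protocol but fall outside every by-arm AE table in the SAP, and the SAP does not declare the change

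*Protocol*

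**What the plan says.** The protocol's definition has a start and no end (7.6.11.10): "AEs reported after the initial dose of randomized study drug will be considered treatment-emergent adverse events (TEAE". Section 9.11.1 refers back to it for the analysis: "Of the AEs reported in the eCRF, TEAEs will be used for safety analyses".

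Routine collection does have an end (7.6.11.2): "All AEs will be collected from the time of informed consent through the Follow-Up call". A footnote to the schedule in 3.1 times that call: "Follow-up call should occur ON Day 14 after last dose. In case subject does not respond, three follow-up attempts should be made". Section 7.6.11.8 then adds a duty without a time limit. It covers "Any SAE that occurs after the AE assessment period specified in Section 7.6.11.2 that is considered by the Investigator to be related" to study drug, and requires a report to the sponsor.

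Section 5.9, on a woman who has interrupted or discontinued drug, says: "The subject may continue in the study after agreement with the Investigator".

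The SAP closes the window (10.1): "AEs that occurred from the first dose of study medication up to 14 days after the last dose will be considered treatment-emergent AEs (TEAEs". It then restricts the tables: "Only TEAEs will be counted in the summary tables described below". It also says that all AEs will be listed. SAP Section 13 records one safety change, the replacement of Clopper-Pearson intervals by intervals for the between-arm difference. Protocol 9.1 requires departures from the protocol analyses to be specified in the SAP with the reason.

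**The concern.** The two definitions disagree on any event that starts on day 15 or later after the last dose, and the SAP version decides what is tabulated. Safety relative to placebo is Primary Objective 2. The overview and the serious-event table are where a reader compares serious events between arms; a by-subject listing gives no such comparison. SAEs are few enough in a 12-week trial that single events can be noticed. If women stop drug more often on one arm, the events left out would not be balanced either.

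**Working it through.** The plan gives no figure for this point, so there is none to reproduce. The check is a comparison of texts, followed by a small calculation of size.

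**1. Follow one SAE with onset on day 15 or later after the last dose.**

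| Question | Protocol | SAP |
|---|---|---|
| Is it collected? | At scheduled visits, yes, whatever its cause (Table 3.1-1, 8.3.1, 8.3.2, 7.6.11.8). After collection ends, only if judged related (7.6.11.8) | 10.1 describes collection up to 14 days after last dose and mentions neither case |
| Is it a TEAE? | Yes (7.6.11.10) | No (10.1) |
| Is it in a by-arm AE table? | Yes, if it is in the eCRF (9.11.1) | No: not in the overview, the SOC/PT tables, the serious-event table or the severity and outcome table |
| Is it listed? | Yes (9.11.1) | Yes, if it is in the data (10.1) |

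**2. Where such events can come from.**

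- Women who stop drug permanently and stay in the study (5.9). Let L be the study day of the last dose. The SAP window closes on Day L + 14, and the Week 12 target is Day 85 (SAP Table 1). Scheduled participation outside the window lasts 85 - (L + 14) = 71 - L days, so it exists only if L is below 71. For example, with L = 21 the window closes on Day 35. That leaves 71 - 21 = 50 days (Days 36 to 85), which contain both the Week 8 (Day 57) and Week 12 visits. A woman who interrupts and resumes has a later last dose and is covered.
- A follow-up call that is reached only after Day 14. The protocol collects through the call; the SAP window has already closed.
- Late related SAEs under 7.6.11.8. The duty is to report to the sponsor. Neither document says that these reports enter the eCRF or the analysis data.

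**3. Is the change declared?** Protocol 9.1 asks for it. SAP Section 13 lists only the confidence-interval change, which itself alters 9.11.1, the section that relies on the TEAE definition.

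**4. Size of one event on the scale the SAP reports.** Assumptions: n = 300 per arm (the planned size) and Wald limits. SAP Section 10 names the FREQ procedure with RISKDIFF but not the type of interval. With p1 for ospemifene and p0 for placebo, d = p1 - p0, SE = sqrt[p1(1 - p1)/n + p0(1 - p0)/n], and the limits are d ± 1.96 SE.

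- 0 v 0: d = 0.00%, limits 0.00 to 0.00. The zero width is an artefact of the Wald formula.
- 1 v 0: d = 1/300 = 0.33%; SE = sqrt(0.003333 × 0.996667 / 300) = 0.00333; 1.96 SE = 0.65%; limits -0.32% to 0.99%.
- 0 v 1: d = -0.33%, limits -0.99% to 0.32%.

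One uncounted event thus shifts the difference by a third of a percentage point, in either direction.

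**The case against.** The best defence is that 14 days is the protocol's own horizon. AEs are collected through a call set for Day 14, withdrawn women are followed for 14 days (7.7), the Follow-up Period is 2 weeks, and the synopsis summarises TEAEs over the Treatment and Follow-up Periods and leaves details to the SAP. On that view the SAP only writes down an implied limit. This stands for routine collection, and it is a good reason to keep the 14-day rows. It does not cover women who remain in scheduled visits after stopping. For them, 7.6.11.2 read strictly ends collection at the call, but the visit schedule still assesses AEs, and 7.6.11.8 requires SAEs during the study to be reported regardless of cause.

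A second objection is that a row of all late SAEs would mix systematic capture with reports made only because the investigator suspected the drug. That also stands, and a between-arm interval on such a mixture would be hard to interpret. The answer is to separate the two kinds of event.

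Three stronger readings are tempting, and the documents do not support them:

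- A reader might infer that late SAEs are lost. All AEs are to be listed, so those in the data remain visible.
- A reader might infer that the death row misses late deaths. The SAP window applies to when the AE occurred, and ongoing AEs are followed beyond 14 days (7.6.11.2, 7.7). An AE that starts inside the window and later proves fatal still counts. Only events that start after the window are left out.
- A reader might take one-arm exact limits (1.22% for 0/300, 1.84% for 1/300) and say that the upper limit is understated by about 0.6 points. The SAP no longer reports those limits, and an omitted placebo event would move the difference the other way.

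**Conclusion.** The inconsistency is real and undeclared: the protocol counts these SAEs as treatment-emergent, and the SAP tables leave them out. The practical reach is narrow. It is mainly women who stop permanently before about Day 71 and stay in the study, with smaller contributions from late follow-up calls and from post-collection related SAEs if these reach the analysis data. The documents give no expected number, which may be zero, and no basis for a direction of bias. Each event would move the reported difference by about 0.33 percentage points, given 300 per arm and Wald limits. This is a worthwhile low-cost correction to the safety tables, not a threat to the safety objective.

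**What to change.** - Keep the 14-day TEAE rows as they are.
- In SAP 10.1, add to the overview (item 1) and the serious-event table (item 3) a separate by-arm row for SAEs with onset after the first dose, whatever the time since the last dose. Split it in two: SAEs collected during scheduled study participation, with the difference and 95% CI; and SAEs reported after collection ended because they were judged related, as counts only, since their ascertainment is selective.
- For women who continued past Visit 5, apply the SAP's existing split at Visit 5 to the new row, so that the short-term and long-term assessments stay apart.
- State in the SAP that SAEs reported under Protocol 7.6.11.8 are reconciled into the analysis data.
- List the 14-day limit in SAP Section 13 as a change from Protocol 7.6.11.10 and 9.11.1, with the reason.

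The cost is one split row in two tables, a few sentences, and a small reconciliation between sponsor SAE reports and the analysis data. The drawback is that the latest events are captured less systematically, which the split makes visible.
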